Subjects 2-6 years of age are not required to participate in a hotel study. Instead, they will participate in an out-of-home study for 5 consecutive days, 4-6 hours per day. During that 5 day period, subjects should engage in significant activity/exercise. Such activities could include utilizing gym play areas appropriate for toddlers and young children, swimming, and playground games. Evidence of geographic location and exercise/activity will be documented by daily photograph. In addition, investigational center staff will be present daily for the 4-6 hours of exercise during the 5 day period.

Auto Mode Frequent Sample testing

While in Auto Mode, subjects 7-13 years of age will undergo daytime and/or nighttime Frequent Sample Testing (FST) during the Hotel study with i-STAT® used as a reference value.

Subjects 7-13 years:

Overnight frequent sample testing (10PM to 7AM) in Auto Mode will be every 30 minutes; daytime frequent sample testing (7AM to 10PM) in Auto Mode will be every 60 minutes. The exact times of FST may differ, but the interval for testing should remain as described.

Subjects 2-6 years:

During one of the days of the out-of-home study subjects should undergo frequent sample testing for 4-6 hours using SMBG as a reference method. The frequent sample testing period will be supervised by investigational center staff. Frequency of testing is every 30 minutes. .

Note 1: The Auto Mode Frequent Sample Testing may be performed at any time during the hotel study (7-13 years) or the out-of-home study (2-6 years).

Note 2: It is important that calculation of total blood draw be maintained throughout the study so that the total amount of blood volume does not exceed the maximum each subject is allowed. If the maximum is reached, FST will be stopped.

All participating investigational centers will target 3-6 subjects (7-13 years) to undergo a hotel study on Day 7 to Day 14 in Month 1 of the study period. On Days 1-6 of the Study period, during which data necessary for Auto Mode initiation is collected, subjects will not be permitted to turn Auto Mode ON. Entry into Auto Mode will occur on day 7 whether at home or in hotel. A minimum of 4 subjects are recommended to participate in each of the hotel studies. However, the sponsor has discretion to allow more or less subjects to attend a hotel stay should the site request this.

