8.2. Study Period Visits: This period lasts 96 - 110 days

Overview

[figure not shown]
- All enrolled subjects will be asked to participate in 1 of the hotel studies
 - Subjects who cancel or are otherwise unable to participate in the hotel study may be re-scheduled for the next available hotel study
- Each site will target 6 subjects who must come in for the Hotel Study on Day 1 - Day 6 in Month 1 of the study period
 - If site has less than 4 subjects for a Hotel study the sponsor will determine whether or not the Hotel Study should proceed.
- Remaining subjects will be assigned to participate in the hotel study(ies) during Month 2 (Day 36- Day 66) or Month 3 (Day 67- Day 96)
- Telephone Visit windows are counted from the start of the study period (Day 1)
- Sponsor may guide the speed of enrollment during the study

Visit Schedule:

Hotel Visit Month 1 Cohort Schedule

- Office Visit Day 1 - Study Period Alignment Visit
- Hotel Study (Day 7- Day 14)
 - Subjects 2-6 years may do FST during this period of time
- Phone Visit (Day 30 – Day 37)
- Office Visit (Day 44 – Day 51)
- Phone Visit (Day 60 – Day 67)
- Phone Visit (Day 74 – Day 81)
- **End of Study** Period (Office Visit): Day 96 - Day 110

Sample visit schedule for subjects completing the Hotel visit in Month 1:

[figure not shown]

Hotel Visit Month 2 Cohort Schedule

- Office Visit Day 1 - Study Period Alignment Visit
- Telephone Visit (option of office visit) Day 7
- Telephone Visit (option of office visit) Day 8
- Telephone Visit (option of office visit) Day 9
- Telephone Visit (option of office visit) Day 10
- Telephone Visit (option of office visit) Day 11

- Telephone Visit (option of office visit) Day 12
- Telephone Visit (option of office visit) Day 13
- Hotel Study (Day 36 – Day 66)
 - Subjects 2-6 years may do FST during this period of time
- Post Hotel Phone Visit:
 - This Phone visit is to occur within 5 days from the last day of the Hotel study.
- Phone Visit (Day 36 – Day 43)
 - Phone visit not required if any of these days overlap period of hotel stay
- Phone Visit (Day 50 – Day 57)
 - Phone visit not required if any of these days overlap period of hotel stay
- Office Visit (Day 66 – Day 73)
- Phone Visit (Day 80 – Day 87)
- **End of Study Period** (Office Visit): Day 96 – Day 110

Sample visit schedule for subjects completing the Hotel visit in Month 2:

[figure not shown]

Hotel Visit Month 3 Cohort Schedule

- Office Visit 1 - Study Period Alignment Visit

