11.5. Study Period Visit Details

11.5.1. Office Visit 5 – Study Period Alignment Visit

The purpose of this office visit is to provide subjects and their parent(s)/guardian(s)/companion(s) with study devices and training. Subjects will wear the device in Manual Mode for 6 days prior to entering into Auto Mode at the hotel or at home. **The use of the Auto Mode feature during the first 6 days of the study period will not be permitted.**

11.5.2. Daily Surveillance for First 14 days During Auto Mode:

Review Pump uploads daily for first 14 days once **subject has entered Auto Mode (CL)**. Therefore, it is important to note the protocol timelines in order to understand when the subject will enter CL.

- Questions to ask when reviewing the report may include:
 - Is the subject's glucose control worse from baseline
 - Is the subject experiencing too much hypoglycemia – for example hypoglycemia at night
 - Is the subject checking glucose

Note: Subjects are required to perform the daily pump uploads during Hotel portions of this study as well

11.5.3. For subjects who are participating in Month 1 Hotel studies:

- Instruct subjects and their parent(s)/guardian(s)/companion(s) that they may not turn ON the Auto Mode function on the study pump prior to Day 7.

11.5.4. For subjects who are participating in Month 2 or Month 3 Hotel studies:

- Instruct subjects and their parent(s)/guardian(s)/companion(s) that they may not turn ON the Auto Mode function on the study pump prior to Day 7.

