11.5.5. Hotel Study (All subjects who are participating in a Hotel/Clinic study)

Overview

- Cohorts
 - Hotel Study Month 1 (Day 7 – Day 14)
 - Hotel Study Month 2 (Day 36 – Day 66)

- Hotel Study Month 3 (Day 67 – Day 96)
- **Duration:** 6 days
- **Location:** Hotel, House or clinic
- **Goal:** Activities in the mornings and afternoons
- **Safety:** All study Safety Criteria apply to hotel study equally.
- **Activity Plan (Exercise and other activities):**
 - Subjects will not be forced or coerced to complete activities if they do not feel they are capable to complete them. Activity intensity may be adjusted so that subjects are able complete the activity.
 - Site research staff will record subject activities, including the types of activity and the time they are performed.
 - Information on subject activity will be collected in eCRF.
 - There will be numerous activity periods throughout each day for a minimum of approximately 4 hour minimum - 6 hours maximum in total per day. It is understood that exercise/activity on the days subjects are doing FST may be limited. For example, subject would not be able to go swimming with IV in their arm. Activity choices may include the following but not limited to:
 - Walking including walking up and down stair case or hiking
 - Shopping
 - Swimming – such as water aerobics, playing in water, water volleyball, marco polo
 - Aerobics
 - Dancing – such as slow dance
 - Any sport activity which involves ongoing physical movement (i.e., tennis, golf, basketball, tee ball or volleyball)
 - Yoga/stretching
 - Biking

Note: Subjects should perform BG check prior to any aerobic exercise and only start to exercise if BG is >120mg/dL.

- **Auto Mode Frequent Sample Testing (i-Stat® reference for subjects 7-13 years of age)**
 - Placement of IV may be performed.
 - Subjects 7-13 years: During one day and one night of the hotel or clinic stay (any day or night may be selected) each subject will undergo FST in Auto Mode.
 - Night time Auto Mode FST will be between 10PM and 7AM (start no earlier than 8PM)
 - Day time Auto Mode FST will be between 7AM and 10PM (start no earlier than 5AM)

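### The overview bullet in the Synopsis timeline and Section 8.2 puts the Month 1 hotel stay on Days 1-6, when Auto Mode is barred; the cohort schedule in those same sections, Section 4 and Section 11.5.5 put it on Days 7-14

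*Protocol*

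**What the plan says.** **The overview bullet.** Section 8.2 sets each site a target of 6 subjects, who "must come in for the Hotel Study on Day 1 - Day 6 in Month 1". The Synopsis, under Study Timeline, carries the same bullet.

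**The cohort schedule.** Below that bullet, in both the Synopsis and Section 8.2, the Month 1 cohort list has an office visit on Day 1 and then "Hotel Study (Day 7- Day 14").

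**The design text.** Section 4 and its Synopsis counterpart say that all centers "will target 3-6 subjects (7-13 years) to undergo a hotel study on Day 7 to Day 14 in Month 1".

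**The hotel procedures.** Section 11.5.5 lists "Hotel Study Month 1 (Day 7 – Day 14") as the first cohort.

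**The Auto Mode restriction.** Section 11.5.1 states: "The use of the Auto Mode feature during the first 6 days of the study period will not be permitted". Section 4 adds: "Entry into Auto Mode will occur on day 7 whether at home or in hotel". Section 11.5.3 tells Month 1 hotel subjects specifically not to switch Auto Mode on before Day 7.

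**What the stay is for.** Section 11.2 gives its purpose as assessing the hybrid closed loop system against a reference value. Sections 4 and 11.5.5 have the hotel frequent sample testing done in Auto Mode with i-STAT as reference. Section 22.1.3 lists the hotel-period endpoints under an Auto Mode evaluation.

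**The concern.** The bullet is current scheduling text and is worded as an obligation. Followed literally, it places the whole stay in the days when the feature under test may not be used. Two things are then at stake.

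The first is data. The protocol describes hotel i-STAT testing only in Auto Mode, so a stay on the bullet's days yields nothing for the hotel endpoints. Section 8.2 asks each subject to take part in one hotel study and describes rescheduling for those who cancel or cannot attend. It does not describe a second stay for those who attended on days when Auto Mode was barred.

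The second is oversight of the first days in Auto Mode. The Month 2 and Month 3 lists have a telephone visit on each of Days 7 to 13. The Month 1 list has none, and it also lacks the post-hotel call that the other two lists contain. That pattern makes sense if Month 1 subjects are expected to be in the hotel around the start of Auto Mode. It does not fit a stay that ends on Day 6.

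**Working it through.** No sample size or power figure is involved. The check compares the stated day windows.

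**Inputs**
- Stay length: 6 days, 5 nights (Section 4; Section 11.5.5 also gives 6 days).
- Auto Mode permitted from Day 7 (Sections 4, 11.5.1, 11.5.3).
- Planned Auto Mode testing per subject aged 7-13: 15 daytime hours + 9 nighttime hours = about 24 hours (Section 11.5.5).
- Day 1 is the start of the study period (Section 8.2, same overview list).

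**Overlap of each window with the days on which Auto Mode is permitted**

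| Source | Month 1 window | Target per site | Days in window | Days of a 6-day stay with Auto Mode permitted |
|---|---|---|---|---|
| Overview bullet (Synopsis timeline, 8.2) | Day 1-6 | 6 | 6 | 0 of 6 |
| Month 1 cohort schedule (Synopsis timeline, 8.2) | Day 7-14 | none given | 14 − 7 + 1 = 8 | 6 of 6 |
| Study Design (Synopsis, Section 4) | Day 7-14 | 3-6 | 8 | 6 of 6 |
| Section 11.5.5 | Day 7-14 | none given | 8 | 6 of 6 |

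A stay on the bullet's days provides 0 of the roughly 24 planned hours.

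**Could Day 1-6 mean the days of the stay itself?** This fits poorly. The bullet ties the days to Month 1 of the study period, the next bullet gives the later stays as study-day windows (Days 36-66 and 67-96), and the same list names Day 1 as the start of the study period.

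**Listed contacts in the first Auto Mode weeks.** With a stay on Days 1-6, the next item in the Month 1 list is the phone visit on Days 30-37. Days 7 to 29 are 29 − 7 + 1 = 23 days with no listed contact. The Month 2 and Month 3 lists have 7 daily calls on Days 7-13, and Month 3 also has an office visit on Days 14-21.

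**What remains in those 23 days.** Uploads are daily for the first 14 days after Auto Mode entry (Section 11.3) and are reviewed daily (Section 11.5.2). From Day 7 this covers Days 7-20; Days 21-29, 9 days, fall back to weekly uploads. An adult companion at night is required throughout the study period.

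**The Month 1 list under the other window.** A stay on Days 7-12 still leaves Days 13-29 (17 days) without a listed contact. A stay starting on Day 8 or 9 leaves the first one or two Auto Mode days at home without a listed call. The contact list therefore needs checking whichever window is kept.

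**The case against.** The best case for leaving the text alone is that the error would be caught. Days 7-14 appear in the Study Design text, in the cohort schedules and in Section 11.5.5. The Month 1 list has an office visit on Day 1. A site that began a stay on Day 1 could not perform the Auto Mode testing and would meet the conflict at once. This stands as a reason to think the harm unlikely. It does not remove the contradiction: the bullet is mandatory in tone and sits in both timelines.

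Three stronger readings are tempting, and the protocol does not support them.

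- *That Section 8.2 as a whole directs sites to Days 1-6.* It does not. Section 8.2 and the Synopsis timeline each contradict themselves, and a site working from the cohort schedule beneath the bullet goes on Days 7-14.
- *That 45 to 90 children would be affected (3 to 6 subjects × 15 sites).* This assumes that every one of up to 15 sites follows the bullet. It also mixes texts, because 3-6 belongs to the Days 7-14 wording while the bullet says 6. Even 6 × 15 = 90 is only a ceiling, and nothing in the document yields an expected number.
- *That the trial's inference or basic safety cover fails.* The hotel endpoints are descriptive. The A1C and sensor time-in-range analyses in Section 24.3 do not use i-STAT data. Daily upload review and the night companion remain, so oversight is reduced, not absent.

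It is also fair to say that 6 versus 3-6 is a small discrepancy: 6 lies within 3-6, both are targets, and Section 4 lets the sponsor allow more or fewer. Section 4 also permits additional hotel studies at sponsor discretion, so a lost stay might be made good, although no route is written for it.

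**Conclusion.** The point holds as a contradiction in operative scheduling text. For a site following the overview bullet, 0 of 6 stay days permit Auto Mode, none of the roughly 24 hours of reference testing can be done in that stay, and the Month 1 list shows no contact for the first 23 days of Auto Mode. For a site following the cohort schedule, Section 4 or Section 11.5.5, the testing loss does not arise.

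The effect is confined to the descriptive Auto Mode hotel endpoints and to the intensity of contact at Auto Mode start; no powered test is touched. The conclusion assumes that the bullet's days are study-period days, as its own wording and neighbouring bullets indicate. How many subjects would be affected cannot be derived from the document. The text should still be corrected, because the instructions cannot all be followed and the correction is small.

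**What to change.** Reconcile the overview bullet, in both the Synopsis timeline and Section 8.2, with the Month 1 cohort schedules, Section 4 and its Synopsis counterpart, and Sections 11.5.1 and 11.5.5. One Month 1 window and one target number per site should be stated throughout, consistent with the protocol's own Auto Mode restriction. Then check the Month 1 contact list against the window kept, and send sites a clarification.

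The cost is the same one-line correction in two places, plus the site clarification. Reconciling the bullet itself adds no visits, staff or analyses.

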11.2. Study Period Synopsis

Window of 96-110 days from end of Run-in Visit 4 to End of Study for each subject.

Overview:

The 3 month study period is to determine safety of the use of the Hybrid Closed Loop algorithm with the study devices. Subjects will have study devices for 3 approximately months which includes a hotel study either in month 1 (at the beginning of the study) or months 2 or 3. The Hotel study portion is to assess the hybrid closed loop system against a reference value during the day and night, and with daily exercise/activity and unrestricted eating. Safety measure will

include daily pump uploads for first 14 days during Auto Mode, as well as parent(s)/guardian(s)/companion(s) and DSMB oversight.

Study Period Device Procedures

- **Devices Worn:**
 - Study Pump
 - Subjects 2-13 years of age: Sensor is inserted by subject or with assistance from their parent(s)/guardian(s)/companion(s) into either the abdomen or buttocks and connected to GST3C Transmitter
- **Calibration Requirements with Study Meter:**
 - Approximately 30 minutes to 2 hours after the Sensor is initialized, the Study Pump will alert the user to enter meter BGs to perform initial calibration.
 - After the first calibration, the user must calibrate the Sensor within 6 hours of the first calibration.
 - The user must calibrate when prompted by the study pump via the Smart Cal feature
 - The user must calibrate every 12 hours after last calibration.
 - Recommend 3-4 calibrations per day
 - Other recommendations:
 - Always have clean dry fingers when you check your blood glucose
 - Only use your fingertips to obtain blood samples for calibration
- **Auto Mode Settings:**
 - High Setup limit recommended to be set at 300 mg/dL
 - Alert setting options may be set per investigator discretion
 - Low Setup limit recommended to be set at 70 mg/dL
 - Low Setup Limit may not be set lower than 65mg/dL
 - For subjects 2-6 years of age, Low Setup Limit should be set at 80mg/dL and no lower than 70mg/dL
 - The target for the closed loop algorithm is set at 120 mg/dL.
 - A temporary target may be used when subject exercises.
 - Alarms that are fixed into system:
 - Sensor glucose at or below 50 mg/dL
 - When sensor glucose at or above 300 mg/dL for one hour
 - When sensor glucose at or above 250 mg/dL for 3 hours
- **Manual Mode Settings:**

- High Set up Limit recommend to be set at 300 mg/dL
 - Alert Setting Options may be set per investigator discretion
- Low Set up Limit recommend to be set at 70 mg/dL
 - Low Setup Limit may not be set lower than 65mg/dL
 - For subjects 2-6 years of age, Low Setup Limit should be set at 80mg/dL and no lower than 70mg/dL
- Predictive alerts and rate of change alerts are optional
- It is recommend (optional) to have the SmartGuard Low Management turned ON with suspend before low activated and a low limit set at 70 mg/dL
- Please note that the basal insulin rate setting in Manual mode may need to be adjusted due to changes in insulin sensitivity when using Auto Mode. For example, the average hourly basal rate setting may be calculated by multiplying 35%-40% or less (i.e., ages 2-12 years old may require less basal insulin) by the Total day dose and dividing by 24 = XX Units/hour
- **Monitoring Method:**
 - Hotel Study: i-STAT

11.3. Visit Schedule tables

Study Activities (Site Staff Activities)	Screening Visit 1	Visit 2	Visit 3 (Start Run-in)	Visit 4 (End Run-in)	Visit 4B Follow-up Call	Visit 5 (Start Study Period)	Study Period Interim Office Visit	Study Period Phone/Office Visits	Study Period Hotel/House or Clinic/ Out-of-Home Study	End of Study Period Visit	Continuation Period Visits
Informed Consent/Assent Process	X										
Screening Labs ¹	X										
Subject Eligibility Assessment	X										
Obtain demographic and baseline characteristics including ² 
 ○ Age ○ Gender ○ Race (US only) ○ Ethnicity (US only) ○ Prior medical history ○ Duration of diabetes mellitus ○ Height ○ Weight ○ Percentage of time using real- time CGM based on subject report: 
 ○ Within 1 month from time of screening visit ○ Within 2 months from time of screening visit ○ Within 3 months from time of screening visit ○ If subject is already enrolled and is past Visit 1, site may collect this information at a later visit. 	X										
Collect concomitant medication data	X										
Questionnaires (DTQ Baseline)		X									
Questionnaires (DTQ End of Study Period)										X	
Questionnaires (Satisfaction – End of Study Period)										X	

CEP302DOC: Pivotal Pediatric Hybrid Closed Loop Study

CEP302DOC

Revision J

Page 47 of 102

Study Activities (Site Staff Activities)	Screening Visit 1	Visit 2	Visit 3 (Start Run-in)	Visit 4 (End Run-in)	Visit 4B Follow-up Call	Visit 5 (Start Study Period)	Study Period Interim Office Visit	Study Period Phone/Office Visits	Study Period Hotel/House or Clinic/ Out-of-Home Study	End of Study Period Visit	Continuation Period Visits
Ask subjects and parent(s)/guardian(s) about the occurrence of adverse events 
 Record adverse events on the appropriate eCRF, if subject reports health status changes that result in a new medical condition or deterioration of an existing medical condition 		X	X	X	X	X	X	X	X		X
Register subjects in CareLink Clinical ³		X									
Upload the study pump during office visit		X	X	X		X	X	X	X	X	X
Review EZ reference guide ⁴		X	X	X		X	X	X	X	X	
Perform control solution testing - Study Meter(s) ⁵		X	X	X		X	X		X		
Perform control solution testing - Ketone meter ⁶		X							X		
Provide subjects and parent(s)/guardian(s) with study reference materials, e.g. Pump User Guide, Getting Started Guide, EZ reference guide, etc.		X									
Provide The ADA handbook: Insulin Pumps and Continuous Glucose Monitoring: A User's Guide to Effective Diabetes Management; Copyright American Diabetes Association, Inc. (Kaufman F, 2012) ⁷		X									
Disburse informational flyers to parents of pediatric subjects to be provided to school staff if questions about study devices or their function should arise		X									
Print CareLink Reports to include (at minimum) subjects' device settings at each study visit.		X	X	X		X	X		X		
Ask subjects and parent(s)/guardian(s) about device performance issues and if they called the 24 -Hour HL to report them		X	X	X		X	X	X	X	X	X
Provide subjects and parent(s)/guardian(s) with the opportunity to bring up study-related questions and concerns.		X	X	X	X	X	X	X	X	X	X
Supervise subjects as a Sensor is self- inserted or with assistance from parent(s)/guardian(s)/companion(s) into abdomen or buttocks as per labeling instructions ⁸			X	X							

CEP302DOC: Pivotal Pediatric Hybrid Closed Loop Study

CEP302DOC

Revision J

Page 48 of 102

Study Activities (Site Staff Activities)	Screening Visit 1	Visit 2	Visit 3 (Start Run-in)	Visit 4 (End Run-in)	Visit 4B Follow-up Call	Visit 5 (Start Study Period)	Study Period Interim Office Visit	Study Period Phone/Office Visits	Study Period Hotel/House or Clinic/ Out-of-Home Study	End of Study Period Visit	Continuation Period Visits
Connect Sensor to Transmitter			X								
Remind subjects and their parent(s)/guardian(s)/companion(s) to bring in the Study Meter for meter operation testing (with control solution per IFU) to each office visit.		X	X	X		X	X		X		
Evaluate sensor wear compliance (End of Run-in Period)				X							
Review weekly surveillance reports		X	X	X		X	X	X	X	X	
Perform overnight Frequent Sample Testing of the Low Management Suspend before Low feature: Refer to Section 11.4, the Low Management FST Procedure Guidelines and the Low Management FST Discharge Guidelines for further information				X							
Discuss/Schedule dates for the Hotel component of the study; discuss Logistics and all other requirements as applicable		X		X		X	X				
Supervise (in person) exercise activities during each day of the 5-day Out-of-Home study for subjects 2-6 years of age. Follow separate instructions for exercise start/stop.									X		
Additional A1C Test						X				X	X
Enter eCRFs into the study database as appropriate	X	X	X	X		X	X	X	X		
Schedule the next visit date and time	X	X	X	X		X	X	X	X		X
Inform subjects that observation by Sponsor may occur at any time during study at an office visit or Hotel stay	X										
Measure subject weight (End of Study)										X	
Provide subjects 7 years and older the opportunity to participate in a transition program for the 670G pump and the Guardian Link Transmitter (US Only)										X	
Return subject to personal standard of Care (End of Study)										X	
Provide information about continued access to study devices for a period of up to 3 years. Participation in the program is optional										X	

¹ Screening labs include: A1C, Creatinine, TSH, Free T3, Free T4, Pregnancy test (urine/serum)

Note regarding A1C: *Specimens collected for A1C testing will be sent to and tested by a NGSP certified Central Laboratory; A1C testing must follow National Glycohemoglobin Standardization Program (NGSP) standards*

Note regarding TSH Testing (local lab): Initial test is TSH; If the TSH level is out of range, Free T3 and Free T4 will be tested; Subject may be included with TSH out of range as long as: a) Free T3 is low or within the normal reference range and b) Free T4 is within the normal reference range; TSH, including Free T3 and Free T4, may be repeated once within 14 days of screening for values that are out of reference range; 7 additional days may be added to the run-in period window for subjects who repeat thyroid function tests

Note regarding Urine pregnancy testing: Collect Urine pregnancy test for female subjects of child bearing potential

² Body Mass Index (BMI) will be calculated automatically in the study database, based on height and weight measurements entered.

³ CareLink Registration:

- Subjects' study information will be entered and subjects will select a password.
- Subject information will be documented on the investigational center's Subject Contact Log (see Investigator/Site binder for details).
- Subjects will use their ID/Password throughout the study;
- Investigational centers will use individual ID/Passwords to access subjects' CareLink account for study purposes

⁴ EZ Reference guide Details

- Phone number(s) of study staff and the after-hours telephone number(s) for the study doctor(s) who are assigned to respond to calls from subjects who have questions or experience problems.
- Reporting device issues to 24 Helpline
- Completing electronic diary for use-related issues not requiring 24 Helpline Assistance
- Subjects and parent(s)/guardian(s) will be requested to call study staff if they have glucose levels above 300 mg/dL with elevated ketone levels accompanied by nausea, vomiting, or inability to drink fluid.
- Ketone testing requirements

⁵ **Study Meter:** If the Study Meter reading falls outside the stated control solution (control solution for Study Meter is investigational must only be used with the Bayer meter) range, then testing with new test strip(s) will be repeated until the reading falls within the appropriate control solution range (see Study Meter user guide materials). If a Study Meter's reading remains outside the control solution range after 3 attempts, a new Study Meter will be provided.

⁶ **Ketone Meter:** If the Ketone Meter reading falls outside the stated control solution (control solution for Ketone Meter is specific to device) range, then testing with new test strip(s) will be repeated until the reading falls within the appropriate control solution range (see Ketone Meter user guide materials). If a Ketone Meter's reading remains outside the control solution range after 3 attempts, a new Ketone Meter will be provided.

⁷ One handbook will be provided per subject and parent(s)/guardian(s)/companion(s); the handbook will be reviewed for the following:

- Train subjects and their parent(s)/guardian(s)/companion(s) on the devices as well as diabetes management principles such as the treatment of hyperglycemia or hypoglycemia and having access to oral glucose in case of hypoglycemia.

- Instruct subjects and their parent(s)/guardian(s)/companion(s) to change infusion sets when infusion set catheter occlusion is suspected. Insulin via syringe may need to be given, especially if ketones are present.
- Review general pump management with parent(s)/guardian(s)/companion(s). It is understood that in order to be eligible for the study, patients must be pump users. This part of training will be a refresher.

⁸ Sensor Details:

- The sensor must be calibrated to ensure correct operation.
- The Investigator may allow a subject to leave the center prior to sensor initialization.
- If subjects encounter any calibration problems with the sensor, the sensor may be replaced to ensure correct operation.
- Subjects, with the assistance of parents/guardians, should replace the sensor after 7 days of use (upon receiving a “Sensor expired” alert) or as events dictate throughout the course of the study.

Study Activities (Training and Instruction)	Screening Visit 1	Visit 2	Visit 3 (Start Run-in)	Visit 4 (End Run-in)	Visit 5 (Start Study Period)	Study Period Interim Office Visit	Study Period Phone/Office Visits	Study Period Hotel/House or Clinic	End of Study Period Visit	Continuation Period Visits
Train subjects and their parent(s)/guardian(s)/companion(s) on the use of the 670G study pump		X								
Instruct/Remind subjects to replace the pump battery 3 times per week		X	X		X	X	X	X	X	X
Instruct/Remind subjects to wait at least 10 minutes to insert the new battery after removing the used battery. This should occur at least once per month.		X	X		X	X	X	X	X	X
Train subjects, their parent(s)/guardian(s)/companion(s) on the use of the Study Meter, according to the Study Meter’s user guide		X								
Instruct subjects, their parent(s)/ guardian(s)/ companion(s) on the use of the bolus calculator (for meal and/or correction doses)		X								
Train subjects and their parent(s)/guardian(s) on how to upload the pump ¹		X								
Train subjects and their parent(s)/guardian(s) on the use of CareLink		X								
Train subjects, their parent(s)/guardian(s)/companion(s) on the use of the ketone meter, according to the ketone meter’s user guide		X								
Train subjects on the EZ Reference Guide		X								

CEP302DOC: Pivotal Pediatric Hybrid Closed Loop Study

CEP302DOC

Revision J

Page 51 of 102

Study Activities (Training and Instruction)	Screening Visit 1	Visit 2	Visit 3 (Start Run-in)	Visit 4 (End Run-in)	Visit 5 (Start Study Period)	Study Period Interim Office Visit	Study Period Phone/Office Visits	Study Period Hotel/House or Clinic	End of Study Period Visit	Continuation Period Visits
Instruct subjects and parent(s)/guardian(s) that they must have a parent(s)/guardian(s)/companion(s) for the duration of the study period (starting at Visit 4 - End of Run In) ²		X								
Instruct subjects and their parent(s)/guardian(s) to enter blood Ketone Meter values, if collected, into CareLink weekly (every 7 days) – see EZ Reference Guide		X								
Instruct subjects and their parent(s)/guardian(s) about ketone-related reporting requirements and actions to be taken in response to symptoms, (see EZ reference guide)		X	X	X	X	X	X	X		
Train subjects and their parent(s)/guardian(s)/companion(s) on CGM, the proper use of the Sensor and the Study Pump. The investigator or qualified research staff will provide recommendations whether or not the sensor glucose low and high alerts should be turned on or off and, if turned on, at which threshold they should be set.			X							
Instruct subjects on sensor calibration requirements ³			X							
Train subjects on Run-in Period requirements ⁴			X							
Instruct subjects and their parent(s)/guardian(s)/companion(s) that sensors must be worn continuously throughout the study and that successful sensor wear with pump CGM will be a condition for continued study participation			X	X	X	X	X	X		
Instruct subjects and their parent(s)/guardian(s)/companion(s) to check blood glucose at least 4-6 times per day for diabetes self-management (SMBG), using the supplied Study Meter according to the user guide. Subject compliance with SMBG will be encouraged and will be used at the end of the run-in period to determine whether or not subjects are suitable to move into the study period		X	X	X	X	X	X	X		
Train subjects and their parent(s)/guardian(s)/companion(s) on the Auto Mode feature of the study pump					X					
Train subjects and their parent(s)/guardian(s)/companion(s) on specific considerations regarding Auto Mode ⁵					X					

CEP302DOC: Pivotal Pediatric Hybrid Closed Loop Study

CEP302DOC

Revision J

Page 52 of 102

Study Activities (Training and Instruction)	Screening Visit 1	Visit 2	Visit 3 (Start Run-in)	Visit 4 (End Run-in)	Visit 5 (Start Study Period)	Study Period Interim Office Visit	Study Period Phone/Office Visits	Study Period Hotel/House or Clinic	End of Study Period Visit	Continuation Period Visits
Instruct subjects and their parent(s)/guardian(s)/companion(s) that they should not assume that Auto Mode is able to prevent all hypoglycemia or all hyperglycemia including diabetic ketoacidosis					X					
Instruct/Remind subjects that the use of Acetaminophen is not allowed during the study 
 If acetaminophen is taken, subjects will be instructed to use additional BG meter readings (they are not to calibrate with those readings) to verify their glucose levels. Subjects will be instructed to exit AutoMode 					X	X	X	X	X	
Instruct subjects and their parent(s)/guardian(s) that the investigational center staff will receive surveillance reports from the Sponsor which identify non-compliant subjects who may be using the Auto Mode function. If this occurs, the subject should be withdrawn (See Withdrawal Procedures, Section 18)			X		X					
Out-of-Home study (subjects 2-6 years of age): Instruct parent/guardian to take appropriate measures regarding high and low blood sugars during the Out-of-Home study. Provide appropriate training materials.					X					
Out-of-Home study (subjects 2-6 years of age): Discuss with subjects and parent(s)/guardian(s) the plan for the Out-of-Home study, e.g. staff will be performing SMBG testing and will need to coordinate with the family.					X					
Hotel/House/Clinic Study (7-13 years): Discuss with subjects and parent(s)/guardian(s) the plan for the hotel stay, e.g. ground rules, availability of staff, Logistics, etc.					X					
Hotel/House/Clinic Study: Instruct subjects and parent(s)/guardian(s) about the requirements for overnight FST testing with i-STAT® as reference, e.g. frequency, duration, etc.					X			X		
Hotel/House/Clinic Study (7-13 years): Communicate that Parent(s) or Guardian(s) should be present during hotel study. Immediate family members may attend hotel stay.					X			X		

CEP302DOC: Pivotal Pediatric Hybrid Closed Loop Study

CEP302DOC

Revision J

Page 53 of 102

Study Activities (Training and Instruction)	Screening Visit 1	Visit 2	Visit 3 (Start Run-in)	Visit 4 (End Run-in)	Visit 5 (Start Study Period)	Study Period Interim Office Visit	Study Period Phone/Office Visits	Study Period Hotel/House or Clinic	End of Study Period Visit	Continuation Period Visits
Instruct subjects and parent(s)/guardian(s) that they should call the investigational center as soon as possible with any changes to their health status (adverse events) - see EZ reference guide		X	X	X	X	X	X	X	X	X
Instruct subjects and parent(s)/guardian(s) that they should keep their own insulin pump supplies in a safe place in case they should be asked during the study to revert back to their own pump		X								
Instruct subjects and parent(s)/guardian(s) that they should always have back up to their study pump on hand such as insulin and syringe in case of study pump issue (e.g. infusion set occlusion with high glucose)		X								
Instruct subjects and parents to report to the investigator any time the device could not be worn due to a device performance issue		X	X	X	X	X	X	X	X	X
Instruct subjects and their parent(s)/guardian(s) that they will be required to source their own insulin. As indicated in inclusion criterion # 13 all subjects must agree to provide and use one of the following rapid acting u100 insulin brands: 
 Humalog® (insulin lispro injection) NovoLog® (insulin aspart) 		X								
Instruct subjects and their parent(s)/guardian(s) to contact the Medtronic 24-Hour HelpLine (HL) in the event they experience problems with their study devices. The 24-Hour HL will be able to assist with troubleshooting and answer questions (Call number provided on EZ reference guide)		X	X	X	X	X	X	X	X	X
Instruct subjects and their parent(s)/guardian(s) to contact the investigational center (Call number provided on EZ reference guide) for therapy related questions including changes in pump settings		X	X	X	X	X	X	X	X	X
Instruct subjects and their parent(s)/guardian(s) to complete the electronic diary for any for use-related issues not requiring 24 Helpline Assistance (web access provided on EZ reference guide)		X	X	X	X	X	X	X	X	X
Instruct subjects and their parent(s)/guardian(s) to always base their diabetes therapy decisions on a confirmatory finger stick (per user guide). In this study, finger stick measurements will be used exclusively; no alternate site testing will be allowed		X								

Study Activities (Training and Instruction)	Screening Visit 1	Visit 2	Visit 3 (Start Run-in)	Visit 4 (End Run-in)	Visit 5 (Start Study Period)	Study Period Interim Office Visit	Study Period Phone/Office Visits	Study Period Hotel/House or Clinic	End of Study Period Visit	Continuation Period Visits
Instruct subject's parent(s)/guardian(s)/companion(s) on administration of glucagon and when to give it to subject		X								
Train subjects and their parent(s)/guardian(s)/companion(s) to try to give meal bolus of insulin 10-15 minutes prior to meal for entire study as much as possible		X								
Remind subjects and their parent(s)/guardian(s)/companion(s) to verify appropriate meter operation for both the Study Meter and the Ketone Meter during home use. The respective user guides should be consulted to determine frequency of testing		X	X	X	X	X	X	X		

¹ Pump and Study Meter Uploading requirements:

- Uploads must occur weekly for the entire run-in period
